Family members appear to play a significant role in encouraging Veterans with SUDs to engage in treatment. In general, Veterans tend to welcome family members' involvement in care for medical and mental health problems [7-9] and report that improving relations with family members are significant reasons for entering treatment [10]. As a response, in June 2011 VA launched *Coaching Into Care* (CIC) [11] a national call center whose goal is to help the family members and friends of Veterans who believe that the Veteran in their lives needs mental health or substance abuse treatment. Typically, callers are concerned about the functioning of a Veteran who is reluctant to seek care. CIC has developed a manualized, flexible telephone-based coaching strategy that consists of social support, problem solving, communication training, and referral in working with callers, usually over a series of telephone calls (see Appendix). Initial quality assurance data suggest that CIC services lead to an increase in treatment seeking (see Preliminary Studies). Unfortunately, our data also indicate that family members calling about a Veteran with substance misuse have a greater difficulty in encouraging the Veteran to seek care.

Our goal is to enhance the usual CIC coaching strategy using a variant of an intervention that has strong empirical support, the Community Reinforcement and Family Training (CRAFT). CRAFT is a face-to-face intervention that was designed to increase the likelihood that an individual with an SUD will seek treatment through positive reinforcement. CRAFT works with a concerned significant other (CSO) as the client. An initial step is to help the CSO with safety planning to reduce the risks of relationship violence, especially when the Veteran is not sober. A major goal is to help the CSO make changes to reinforce clean and sober behaviors (e.g., spending time with the Veteran only when he or she is sober). The intervention helps the CSO decrease inadvertent support for substance/alcohol misuse (i.e., cease being attentive when the Veteran is hung-over from drinking). It also supports the CSO so he or she can help the Veteran enter treatment when the Veteran signals readiness for treatment. Finally, CRAFT seeks to reduce the CSO's ineffective coercion toward the Veteran about treatment (e.g., demanding the Veteran get help).

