[name] began CIC in 2010 as a pilot project and continues as the Director. Coaching Into Care has grown significantly since 2011 when it became a national program; in 2014 alone, CIC received over 3000 initial (incoming) calls. About 50% concerned a Veteran from the OEF/OIF/OND eras. About 70% of the calls in 2014 concerned psychosocial issues, including mental health, substance abuse, and/or behavioral concerns that may have an impact on the Veterans' or others' physical safety. Seventy-five percent of the callers were female, with 28% of them being a spouse or other intimate partner, 19% parents, 12% were sons, daughters or siblings, 28% were other types of family members, friends or other relationships. Thirteen percent of the calls were directly from Veterans about mental health, benefits, or other concerns. Virtually all of the callers to CIC have internet access; exceptions tend to be older callers and/or those with lower financial resources.

Quality Assurance (QA) data from our call center operations have indicated that the service is highly rated by callers but the impact of the service may be limited, especially in the cases of substance misuse. Within about 3 months of first calling, the treatment engagement of the Veteran who is the subject of the calls with CIC rises modestly [11]. In 939 CSO callers who started coaching since November 2014 whose concerns were specifically focused on mental health problems and no substance misuse of the Veteran, 248 of the Veterans were engaged in mental health care; this number rose 54% to 382 at follow-up. CSO callers had at least one call with a coach and some had more than 20. For a separate subsample of 109 callers of Veterans with substance misuse who entered coaching, the rate of treatment rose a more modest 40%, or 35 to 49 Veterans in care. In these uncontrolled findings the initial treatment engagement rate of those who entered coaching was somewhat higher for those with substance misuse vs. no substance misuse (34% vs 26%). It does appear, however, that additional systematic strategies are needed for those Veterans with substance misuse problems. See the Appendix for CIC Manuals.

Preliminary feasibility test of the web-based delivery of CRAFT for PTSD

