The Coaching-CRAFT intervention is meant to be a combination of CIC's coaching strategy combined with the didactic material in the recently developed web-based CRAFT intervention, VA-CRAFT [17]. The VA-CRAFT course for substance misuse has 8 modules that follow the original CRAFT intervention [9] (see Appendix 2 for module details): 1) Introduction to CRAFT, 2) Overview of CRAFT, 3) Getting Started with CRAFT: Safety Planning, 4) Understanding substance abuse, 5)

How to respond to substance abuse, 6) How to rebuild your life together, 7) How to help someone consider treatment, 8) Wrapping up. The goals of the intervention include understanding triggers and long-term reinforcement of substance misuse, ignoring unhealthy behaviors and rewarding healthy behaviors, getting support, and how to help the CSO caller help the Veteran enter treatment.

The PI will work with the Key Personnel to discuss the following factors: 1) format of the manual, 2) level of manual detail, 3) optimal pace of work with the CSO using the web-based CRAFT content, 4) optimal number and length of calls, 5) points of individualizing the material in CRAFT to the CSO's specific situation, and 6) the coach's role in identifying appropriate programs and facilitating entry into treatment soon after the Veteran indicates his or her readiness. *The group will meet by conference call regarding these factors, the PI will draft the manual, and the Key Personnel will meet again to discuss the draft. This iterative process will continue until we have a suitable draft manual. We will then seek feedback from volunteer Veterans and their family members at the CPL Michael J Crescenz VA Medical Center (Philadelphia). This feedback will be incorporated and the draft will be discussed again by the Key Personnel and the PI will produce a final draft for the trial.* We will also develop a fidelity scale for the essential targets for the telephone interventionist of Coaching-CRAFT. The manual development will occur in months 1-4.

Clinical Trial

Sample and recruitment procedures

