Intervention acceptability, satisfaction, and engagement. We will measure satisfaction with the intervention using questions used currently by the CIC call center which asks the caller’s expectations of service, helpfulness, changes in hopefulness, and report of the Veterans desire for and engagement in care (see Appendix 2). Additional open-ended questions will assess how the telephone-based support or VA-CRAFT content could be changed to improve convenience, acceptability, or effectiveness. *We also plan to secure a HIPAA waiver to obtain VHA administrative data to verify the CSO’s report of the Veteran’s engagement in VHA care (see Human Subjects).*

We will assess the engagement of the CSO in the intervention by tracking the number and length of telephone calls with the interventionist, and the number of sessions the CSO logs in to use the web-based CRAFT material, *repeat visits to sessions*, and the degree of completion of each of the modules. Drop-outs from the intervention and drop-outs from assessment follow-up will also be carefully tracked. Drop-outs will be defined as no response after 3 attempts over 1 month.

Schedule of Assessments

Measure (source: domain)	Baseline	6 months	12 months
CSO: CSO’s alcohol & substance misuse, Veterans alcohol & substance misuse	Form 90	Form 90	Form 90
Treatment utilization	Form 90	Form 90	Form 90
Burden	Caregiver Burden Scale	Caregiver Burden Scale	Caregiver Burden Scale
CSO Symptoms, CSO perceptions of Veteran’s PTSD symptoms	MINI, PHQ-9, PCL- 5 (family ver.)	MINI, PHQ-9, PCL- 5 (family ver.)	MINI, PHQ-9, PCL- 5 (family ver.)
CSO perceptions of intervention			Open-ended questions
Web-host tracking: Engagement in interventions			Website use (time on sessions, repeat visits to sessions, completion)
Veteran: Vet’s subst. abuse & Treatment			Form 90
Veteran symptoms			MINI, PCL 5, PHQ-9
Veteran perceptions of interaction with CSO			Open-ended questions
Veteran’s MH/SA treatment engagement	Questions about treatment engagement, if/when the Veteran agrees to treatment		VHA administrative data

Trial procedures

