The primary goal of the trial intervention will be a test of the feasibility of Coaching-CRAFT, CSO’s experience and engagement in the intervention, and within-subject estimates of changes in Veterans’ engagement in treatment. We will seek to enter 50 family member callers into a nonrandomized trial over 6 months. Each research-based telephone contact will be audio recorded for examination using the fidelity scale developed in months 1-4.

An additional goal is to compare the outcome in the trial to a usual-care sample of at least 50 CIC callers that have not been offered Coaching-CRAFT, matched on the basis of the Veteran’s primary substance use problem(s), relationship of CSO to Veteran, contact time and co-habiting

status, Veteran age and gender, and race. We will select comparison cases from a several year time-frame to ensure an appropriate comparison.

The length of the active coaching of the CSO using the web-based CRAFT material is anticipated to last no longer than 6 months, but this will be determined by the treatment manual development phase. Additional assessments will occur at 6 and 12 months after study entry and will include the measures as detailed in the table (above). *At 12 months, we will ask the CSO to invite the Veteran to engage in the study and answer study questions about their symptoms, treatment, and the CSO's approach to them.* We will carefully assess the safety and risk to the CSO-Veteran relationship prior to making the decision to pursue this assessment. Working with the CSO, we will ask the CSO to ask the Veteran to be involved, including type of discussion between CSO and Veteran might be helpful, and ask the CSO to ask the Veteran to call the study staff (see Human Subjects).

Timeline

We anticipate the trial will begin in Year 1 with initial recruitment occurring from months 5-10. The trial will end in Year 2, month 22. Analyses of feasibility, satisfaction and treatment engagement will occur in months 19-24. After the formal participation in the trial, any caller who needs additional support or treatment referral will be referred to the CIC call center.

Data Analysis, Sample Size considerations, and intervention modification

Feasibility Outcomes

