We will examine CSOs ratings of the intervention with a criterion of at least 80% of those rating the intervention as helpful, leading to increased hopefulness and preparedness to help the Veteran, and that the intervention had helped the family overall. We will also examine the degree to which the subjective symptoms of distress (PHQ-9, subjective burden), decline over the Baseline, 6 month, and 12 month assessments, using a mixed methods model test of within-subjects change over time. We will compare the completion rates of the Coaching-CRAFT sample of CSOs with a sample of CSOs from the CIC QA data. "Completion" will mean at least 6 months of telephone coaching of 8+ calls. We will match CSOs receiving Coaching-CRAFT with the treatment as usual data (see above).

Intervention comparisons

In a key analysis we will also plan to test the proportion of the Veterans of the CSOs who entered treatment for substance misuse against the matched CSOs from the CIC QA data. We will use an intent-to-treat approach. Those CSOs lost to follow-up will be deemed intervention failures regarding the Veterans' engagement in treatment. We plan to use a basic test of difference between proportions in independent samples (a two sample z-test). To detect a difference between the rate of engagement in treatment using CIC QA data (i.e., 41%) and conservative outcomes drawn from the CRAFT RCTs (67%), the sample group needed to detect a difference with power of 80% in post-intervention treatment engagement outcomes, is $N = 45$, for each group [29]. Our intent-to-treat sample size of $N = 50$ exceeds this number.

Review of CSO and Veteran report: *Qualitative and treatment engagement reports*

We plan to conduct a systematic review of the responses to the post-intervention open-ended questions in order to modify the intervention as needed in preparation for a large RCT. In addition, we plan to assess the rate of Veteran inclusion in the study at 12 months, *the CSO report, the VHA report of Veteran treatment utilization, and the comparison of these different data sources.*

Considerations of alternative approaches

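### The completion definition is not comparable across groups and conflicts with Coaching-CRAFT's own planned length, so the difference in completion rates cannot be read as a difference in retention

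*Combined protocol and SAP*

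**What the plan says.** The Feasibility Outcomes part of the data analysis section contains a between-group contrast: "We will compare the completion rates of the Coaching-CRAFT sample of CSOs with a sample of CSOs from the CIC QA data". The definition follows directly: "Completion' will mean at least 6 months of telephone coaching of 8+ calls". It is given once, with no separate version for usual care, and the comparison callers are the matched QA sample.

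Four other places bear on it:

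- **Usual care.** Background and Significance describes a "manualized, flexible telephone-based coaching strategy", normally delivered over several calls. The call-center part of Preliminary Studies says that callers had from one call to more than 20. No intended length or call target for usual coaching appears in the document.
- **Length of Coaching-CRAFT.** Trial procedures says that active coaching "is anticipated to last no longer than 6 months, but this will be determined by the treatment manual development phase".
- **Number of Coaching-CRAFT calls.** The manual development section lists the "optimal number and length of calls" among matters still to be settled.
- **Drop-out.** The Measures section, under acceptability, satisfaction and engagement, has a separate rule: "Drop-outs will be defined as no response after 3 attempts over 1 month". The completion comparison does not use it.

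**The concern.** A completion rate is informative when each group has a defined course and one asks who reached its end. Here one group has a course whose length and call count are not yet fixed, and the other has no stated course. A duration-and-dose threshold laid over both records the amount of coaching. It does not separate a CSO who stopped answering from one whose need was met, or from one whose Veteran entered treatment, which is the result that both programmes seek. It can therefore score success as failure.

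Feasibility and CSO engagement are part of the trial's primary goal, and this is the only measure under Feasibility Outcomes that has a comparator. A difference in either direction is likely to be read as CSOs being more, or less, willing to stay with Coaching-CRAFT. The study is preparation for a larger randomised trial, so that reading could influence its design.

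**Working it through.** **No figure to reproduce.** The plan gives no expected completion rates, test or sample size for this comparison. Its N = 45 per group concerns treatment engagement only.

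**Step 1: the two lengths side by side.** Let D be the months of coaching for a Coaching-CRAFT CSO.

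- Feasibility Outcomes: completion requires D ≥ 6, plus at least 8 calls.
- Trial procedures: D is expected to be ≤ 6, with the final length left to the manual.

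Both hold only at D = 6. If the manual sets a shorter course, a CSO who finishes all of it is a non-completer.

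**Step 2: how the bar scores different CSOs.**

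| CSO | Dropped out? | Scored by the bar |
|---|---|---|
| Stops responding after three calls | Yes | Non-completer |
| Need met in three calls, coaching ended by agreement | No | Non-completer |
| Veteran enters treatment in month 2, coaching ends | No | Non-completer |
| Finishes a Coaching-CRAFT course set at under six months | No | Non-completer |

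The last row can arise only in the Coaching-CRAFT group. The second and third can arise in either group.

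**Step 3: what this does to the contrast when retention is equal.** Write the completion rate as r × q. Here r is the share of CSOs who stay through their own intended course, set equal in both groups. The factor q is the share whose intended course reaches six months and 8 calls. The model takes r as unrelated to q. The document gives neither quantity, so all values below are assumptions. With r = 0.70:

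| q, Coaching-CRAFT | q, usual care | Coaching-CRAFT | Usual care | Difference (points) |
|---|---|---|---|---|
| 1.00 | 0.25 | 0.70 × 1.00 = 70% | 0.70 × 0.25 = 17.5% | +52.5 |
| 0.50 | 0.25 | 35% | 17.5% | +17.5 |
| 0.25 | 0.25 | 17.5% | 17.5% | 0 |
| 0.25 | 0.50 | 17.5% | 35% | −17.5 |
| 0 (course under six months) | 0.25 | 0% | 17.5% | −17.5 |

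These rows are examples, not bounds. Letting q run from 0 to 1.00 for Coaching-CRAFT and from 0.10 to 0.50 for usual care, the difference r × (q for Coaching-CRAFT − q for usual care) spans:

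- r = 0.60: +54 to −30 points
- r = 0.70: +63 to −35 points
- r = 0.80: +72 to −40 points

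**Step 4: would such a gap be noticed?** With 50 per group and a two-sided 5% z-test (assumed, since none is specified), the chance of a significant result is about 1.00 for 70% vs 17.5%. It is 0.51 for 35% vs 17.5%, whichever group is higher. Since retention is equal in the model, each such result would be an artefact of the definition.

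**The case against.** A reader might infer that the bar favours Coaching-CRAFT by construction, because usual coaching was never meant to run to six months. That can be made to look large. Assume 20% drop-out in both groups, and that half of the usual-care CSOs who stay end early because their need was met. Usual care then scores 0.80 × 0.50 = 40% against 80%. With a quarter ending early it scores 0.80 × 0.75 = 60%, a 20-point gap. The document does not support this reading:

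- The arithmetic allows early satisfied endings in usual care only and assumes that every retained Coaching-CRAFT CSO meets the bar. Equal early endings in both groups give 40% vs 40%. If Coaching-CRAFT brings more Veterans into treatment early, the gap could reverse.
- No Coaching-CRAFT call schedule exists yet, and eight web modules are not eight calls.
- That usual coaching was not meant to reach the bar is an inference from silence. Some callers had more than 20 calls, so eight lies within observed practice. The CIC manuals are in an appendix that is not part of the text reviewed.
- The passage beginning "Within about 3 months of first calling, the treatment engagement of the Veteran" gives the window for the Veteran's outcome. It does not say how long coaching lasted.

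It can also be said that little hangs on this comparison. It carries no test or go/no-go rule, the stated criterion is 80% favourable ratings, the key analysis is treatment engagement, and calls, call length, module completion and drop-outs are already tracked. This limits the consequences but does not make the contrast interpretable.

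Finally, the drop-out rule is written for trial participants. Nothing shows that QA records spanning several years log three contact attempts over a month, or why coaching ended. That stands, and it makes the remedy conditional.

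**Conclusion.** The concern holds in limited form. From the text alone, the completion bar is applied to a comparator with no stated length or call target, so it measures coaching received rather than retention. It counts early success as non-completion. Its six-month floor coincides with the ceiling on Coaching-CRAFT's expected length, and those two passages must be reconciled.

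Size and direction are unknown. The figures in the working rest on assumed values and show only that equal retention can produce a large gap in either direction, or none. They do not estimate a bias and do not support a claim that Coaching-CRAFT is favoured. The treatment-engagement comparison does not use this definition and is unaffected. The plan should be changed, but the point does not undermine the trial as a whole.

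**What to change.** 1. Reconcile the completion definition in Feasibility Outcomes with the expected coaching length in Trial procedures and with the call count that the manual will set. Which length or count is right is for the investigators to decide.
2. Do not use the fixed six-month, 8-call bar as the between-group retention measure.
3. Where the QA logs allow, compare drop-out in both groups over the same period, using the non-response rule already in Measures. An agreed end of coaching, or the Veteran's entry into treatment, should not count as drop-out.
4. Report the distributions of number of calls and coaching duration in both groups.
5. Check beforehand whether the QA logs record contact attempts and reasons for ending. If they do not support the rule, give the call and duration distributions descriptively and make no retention claim.

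The cost is protocol wording and a review of QA call logs. The downside is that the logs may record attempts and reasons less fully than the trial does, and unequal recording could bring in a bias of its own. The change also leaves one limitation in place: consented research participants are compared with routine callers who are not matched on motivation, and that should be stated with any retention result.

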Members of our team are experienced developers of manualized telephone-based interventions for substance abusing populations. Co-I [name] and colleagues have developed a method of monitoring and counseling following acute care for people with alcohol and substance dependence [14, 15]. This manualized treatment has shown efficacy relative to controls in several randomized controlled trials [14-16] (see Appendix 2). In addition, [name] and colleagues have developed an intervention for caregivers of Veterans with dementia to decrease caregiver burden and improve engagement in dementia care. A feasibility pilot has just been completed and will be tested in a VA MERIT award (see biosketch). *[name] (PI) continues as Director of CIC and has experience in developing the manualized coaching procedures currently used by CIC.*

Research Design and Methods

Overview

First, we will develop a detailed manual for Coaching-CRAFT, which will be a telephone-based model of coaching that uses the web-version of the CRAFT intervention already developed and available to the investigators. Second, we will conduct a preliminary nonrandomized feasibility trial of the use of Coaching-CRAFT with a sample of 50 family member callers recruited from the CIC call center. We will select for this trial close family member callers who reach CIC with the concern about an OEF-OIF-OND Veteran in their family whom they believe is in need of treatment for a SUD.

An important goal will be to compare the findings to CIC Quality Assurance (QA) data of callers matched on the type of substance misuse of the Veteran and demographic variables (see Trial Procedures). We propose an uncontrolled trial in order to maximize the intervention sample size and based on the strength of our ability to use existing CIC QA data. We will also conduct a test of the assessment of the Veterans regarding their perception of their family members' involvement in their decisions to seek or not seek care, their actual decisions to seek care, and their current symptoms.

Intervention and manual development process

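### The completion rule sets a 6-month minimum on telephone coaching that the plan expects to last at most 6 months with the web course, so early finishers could be scored as non-completers

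*Combined protocol and SAP*

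**What the plan says.** Feasibility Outcomes says that completion "will mean at least 6 months of telephone coaching of 8+ calls", and that completion rates will be compared between the Coaching-CRAFT CSOs and matched CSOs from the call center's QA data.

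Trial procedures says that "active coaching of the CSO using the web-based CRAFT material is anticipated to last no longer than 6 months", and adds that "this will be determined by the treatment manual development phase". The section on intervention and manual development also leaves the pace of the web work and the "optimal number and length of calls" to that phase. On timing, "The manual development will occur in months 1-4", with "initial recruitment occurring from months 5-10".

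On how the telephone and web parts fit together, the Overview describes "a telephone-based model of coaching that uses the web-version of the CRAFT intervention", while the list of terms in the Background defines Coaching-CRAFT as the sum of call-center coaching and the online course. The only later study contacts with the CSO that the text describes are the 6- and 12-month assessments, including the request to invite the Veteran.

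Drop-out is defined separately, under intervention acceptability, satisfaction and engagement: three attempts at contact within a month without a reply. The same section tracks calls, log-ins and module completion.

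**The concern.** One statement is a floor and the other an expected ceiling, both at 6 months. If they describe the same coaching, a CSO who works through the whole course with enough calls, but in less than 6 months, fails the completion rule for a reason unrelated to engagement. That CSO is not a drop-out either.

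Feasibility and CSO engagement belong to the stated primary goal of the trial, and the results are meant to guide changes to the intervention before a large randomised trial. A completion rate lowered by quick finishers could be misread as poor uptake. The threshold is already fixed while the coaching length is still open, and nothing in the plan ties the threshold to the final manual.

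**Working it through.** The plan gives no expected completion rate and no distribution of coaching length, so there is no figure to reproduce. The check applies the stated rule to the stated lengths.

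Inputs:
- Completer: telephone coaching D ≥ 6 months and calls C ≥ 8 (Feasibility Outcomes).
- Coaching with the web material: W ≤ 6 months, anticipated and provisional (Trial procedures).
- Trial group: n = 50 (Trial procedures).

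**1. If the calls end with the web course.** Then D = W. The conditions D ≥ 6 and D ≤ 6 together leave only D = 6. Applying the rule:

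| Months of coaching | Calls | Scored as |
|---|---|---|
| 3, 4, 5 or 5.9 | 8 or 12 | non-completer |
| 6 | 7 | non-completer |
| 6 | 8 or 12 | completer |

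**2. If calls continue after the web course.** Then D can exceed W. A CSO who finishes the modules at month 4 and is still coached by telephone at month 6 can meet the rule. The problem disappears for every CSO coached that long.

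**3. What the manual could do, under the condition in step 1.** If it sets a 6-month course, the rule can be met by CSOs on schedule and fails only those who finish sooner. If it sets a shorter course, no CSO who finishes on schedule can be a completer.

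**4. Size.** Each CSO scored this way lowers the rate by 1/50 = 2 percentage points, so k of them lower it by 2k points. For assumed values k = 1, 5 and 10, the loss is 2, 10 and 20 points. The documents give no value for k, and it may be zero.

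**5. Which clause binds (illustration).** Assume evenly spaced calls starting at week 0. The 8th call follows 7 intervals, so at intervals of 1, 2, 3 and 4 weeks it falls at week 7, 14, 21 and 28. Taking 6 months as 26 weeks, the 8-call clause is met before month 6 whenever the interval is below 26/7 = 3.7 weeks. The duration clause would then decide completion, but only if duration is also counted from first to last call. If it means time in the coaching programme, that does not follow. The course has 8 modules, but their pace is left to the manual, so this is no estimate of what will happen.

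**The case against.** The strongest reply is that the two statements measure different things. Trial procedures bounds coaching that uses the web material; Feasibility Outcomes counts telephone coaching. The list of terms defines the intervention additively, and the manual is also to set out the coach's part in easing entry into treatment once the Veteran is ready, an event not tied to the end of the course. Calls after the course are therefore a live reading. The call-center manuals are in an appendix outside the text reviewed, and the Coaching-CRAFT manual was still to be written, so the absence of a described follow-on phase is weak evidence. All of this stands, and it is why the point is conditional.

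It is also true that the 6-month ceiling is a forecast, and that both statements can hold at 6 months. This softens the conflict without removing it, because an earlier finisher whose calls stop still fails.

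The same rule would apply to QA callers, whose usual coaching is flexible, so it could lower both rates. That also stands. Finally, no success threshold, named test or sample size rests on completion, and calls, modules and drop-outs are tracked separately. This limits the consequence, but the stated rule can still misclassify a feasibility outcome.

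**Conclusion.** The point holds in conditional form. Unless telephone coaching runs past the web course, the completion rule and the anticipated coaching length overlap only at 6 months, and a CSO who finishes sooner with 8 or more calls is a non-completer but not a drop-out. The cost is 2 percentage points of the Coaching-CRAFT completion rate per such CSO, with the number unknown. It is worth correcting before enrolment, but it is confined to the completion rate and its comparison.

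A reader might infer three stronger things that the documents do not support:
- That the plan contradicts itself outright, so that nobody can complete. The ceiling is provisional, a 6-month course satisfies both statements, and later calls are not excluded.
- That the comparison is biased against Coaching-CRAFT. Coaching durations are given for neither group, so the direction is unknown.
- That the main comparison is compromised. The analysis of Veterans entering treatment does not use completion.

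**What to change.** Once the manual is final (months 1-4) and before enrolment opens in month 5, reconcile Trial procedures with Feasibility Outcomes. State whether telephone coaching continues after the web course, and word completion so that a CSO who finishes the manualised course early is not counted as a non-completer.

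For the comparison with QA callers, apply one pre-stated rule to both groups, such as the 8+ calls already named, and report months of coaching separately as a descriptive measure where recorded. First confirm that the QA records support the rule. The plan's remark on call numbers follows its figures for 939 callers with no substance misuse, and the text does not show what is held for the substance-misuse callers who would be matched.

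The cost is one or two sentences in the analysis section, plus that check; the trial-group data are already tracked. The small downside is that completion no longer includes duration of retention, which the descriptive report covers where duration is recorded. The length of coaching and the number of calls remain for the sponsor to decide.
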